- Major surgery (eg, nephrectomy) less than 28 days prior to the first dose of study drug.
- Anti-cancer therapy less than 28 days prior to the first dose of study drug or palliative, focal radiation therapy less than 14 days prior to the first dose of study drug.
- Presence of any toxicities attributed to prior anti-cancer therapy, other than alopecia, that have not resolved to Grade 1 (NCI CTCAE v4) or baseline before administration of study drug.
- Any of the following laboratory test findings:
 - i) WBC < 2,000/mm³
 - ii) Neutrophils < 1,500/mm³
 - iii) Platelets < 100,000/mm³
 - iv) AST or ALT > 3 x ULN (> 5 x ULN if liver metastases are present)
 - v) Total Bilirubin > 1.5 x ULN (except participants with Gilbert Syndrome, who can have total bilirubin < 3.0 mg/dL)
 - vi) Serum creatinine > 1.5 x upper limit of normal (ULN) or creatinine clearance < 40 mL/min (measured or calculated by Cockcroft-Gault formula)

Objectives and Endpoints:

Table 1.-1: Objectives and Endpoints

Objectives	Endpoints

Primary
 
 • To assess the incidence of high grade (CTCAE v4 Grade 3-4 and Grade 5) IMAEs in participants with advanced or metastatic RCC who are treated with combination therapy of nivolumab 6 mg/kg + ipilimumab 1 mg/kg every 8 weeks alternating with nivolumab 480 mg flat dose every 8 weeks, staggered every 4 weeks (Cohort 1) • To assess the incidence of high grade (CTCAE v4 Grade 3-4 and Grade 5) IMAEs in participants with advanced or metastatic RCC who are treated with combination nivolumab (3 mg/kg) and ipilimumab (1 mg/kg) every 3 weeks for four doses, followed by maintenance nivolumab (480 mg every 4 weeks), in the select subgroups of mRCC participants (nccRCC, asymptomatic brains metastasis, or any histology with KPS 50-60% (Cohorts 2, 3, 4)) 	
 • Incidence of high grade (CTCAE v4 Grade 3-4 and Grade 5) IMAEs

Table 1.-1: Objectives and Endpoints

Objectives	Endpoints

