2 SCHEDULE OF ACTIVITIES

Table 2-1: Screening Assessments (All Participants)

Procedure	Screening Visit ^a	Notes
Eligibility Assessments		
Informed Consent	X	Obtain consent prior to performing any testing for eligibility
IWRS	X	An IWRS will be used to assign participant numbers
Inclusion/Exclusion Criteria	X	
Medical History	X	
Tumor Tissue Samples	X	Sufficient tumor tissue, archival or recent acquisition, (block or minimum of 10 slides; obtained from core biopsy, punch biopsy, excisional biopsy or surgical specimen) available to be received at Central Laboratory.
Safety Assessments		
Physical Examination	X	
Vital Signs	X	Including BP, HR, and temperature. Obtain at the screening visit and within 72 hours prior to first dose
Physical Measurements (including performance status)	X	Height and weight and Karnofsky Performance Status.
ECG	X	Within 28 days prior to first dose
Serious Adverse Event Assessment	X	SAE assessment from the time of consent.
Assessment of Signs and Symptoms	X	Within 14 days prior to first dose
Concomitant Medication Collection	X	Within 14 days prior to first dose
Laboratory Tests	X	CBC with differential, Chemistry panel including LDH, AST, ALT, ALB, ALP, T Bili, BUN or serum urea level, creatinine, Mg, Ca, Na, K, Cl, Glucose, amylase, lipase, TSH, Free T4, Free T3, hepatitis B surface antigen (HBVsAg), and hepatitis C antibody (HCV Ab) or hepatitis C RNA (HCV RNA), within 14 days of first dose.
Pregnancy Test (WOCBP Only)	X	Within 24 hours prior to first dose (serum or urine at the site).

Table 2-1: Screening Assessments (All Participants)

Procedure	Screening Visit ^a	Notes
Efficacy Assessment		
Screening/Baseline Tumor Assessments	X	CT/MRI of the chest, abdomen, pelvis and all known sites of disease and MRI (preferred) or CT contrast-enhanced scan of the Brain within 28 days prior to first dose. CT with oral and intravenous contrast or contrast-enhanced MRI are the preferred imaging modalities. If CT iodinated contrast is contraindicated, a non-contrast CT of the chest, and contrast enhanced MRI abdomen, pelvis and all other known or suspected sites of disease should be imaged. (See Section 7.7.2.3).

^a Some of the assessments referred to in this section may not be captured as data in the eCRF. They are intended to be used as safety monitoring by the treating physician. Additional testing or assessments may be performed as clinically necessary or where required by institutional or local regulations.

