6.1 Inclusion Criteria

Inclusion

1) Signed Written Informed Consent

- a) Participants must have signed and dated an IRB/IEC-approved written informed consent form in accordance with regulatory and local guidelines. This must be obtained before the performance of any protocol-related procedures that are not part of normal participant care.
- b) Participants must be willing and able to comply with scheduled visits, treatment schedule, laboratory testing, and other requirements of the study

2) Type of Participant and Target Disease Characteristics

- a) Advanced (not amenable to curative surgery or radiation therapy) or metastatic (AJCC Stage IV) RCC
- b) Histologically confirmed, previously untreated (treatment-naive) RCC (as defined in [Appendix 3](#)):
 - i) Predominant clear-cell.
 - ii) Non-clear cell histology including:
 - (1).papillary
 - (2).chromophobe
 - (3).translocation associated.
 - (4).collecting duct
 - (5).medullary
 - (6).any pathology unclassified.
- c) No prior systemic therapy for RCC with some exceptions:
 - i) One prior adjuvant or neoadjuvant therapy for completely resectable RCC if such therapy did not include checkpoint inhibitors and if recurrence occurred at least 6 months after the last dose of adjuvant or neoadjuvant therapy.
- d) Participants with brain metastases will be allowed if they are asymptomatic and not on systemic corticosteroids or receiving radiation treatment for at least 14 days prior to beginning protocol therapy. Brain lesion(s) that are < 10 mm or that have been previously irradiated will only be assessed as non-target lesion per RECIST 1.1. Brain lesions that are ≥ 10 mm and that have not been previously irradiated will be assessed as target lesions per RECIST 1.1.
 - i) Participants who are found on screening CT/MRI to have brain metastases will be enrolled to Cohort 3 or 4 (depending on the KPS level) if they do not require active treatment (radiation treatment/corticosteroids)
 - ii) Participants who are found on screening CT/MRI to have brain metastases that require immediate treatment (radiation treatment/corticosteroids) will be re-enrolled to Cohort 3 or 4 (depending on the KPS level) after completing active treatment
- e) Measurable disease as per RECIST 1.1. Participant must have extracranial metastasis as measurable disease ([Appendix 4](#))
- f) Karnofsky Performance Status (KPS) of at least 70% for Cohort 1, 2, and 3; KPS of 50-60% for Cohort 4 ([Appendix 5](#))

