- c) Anti-cancer therapy less than 28 days prior to the first dose of study drug or palliative, focal radiation therapy less than 14 days prior to the first dose of study drug.

3) Physical and Laboratory Test Findings

- a) Presence of any toxicities attributed to prior anti-cancer therapy, other than alopecia, that have not resolved to Grade 1 (NCI CTCAE v4) or baseline before administration of study drug.
- b) Any of the following laboratory test findings:
 - i) WBC < 2000/ μ L
 - ii) Neutrophils < 1500/ μ L
 - iii) Platelets < 100*10³/ μ L
 - iv) Hemoglobin < 9.0 g/dL
 - v) Serum creatinine >1.5 x ULN or calculated creatinine clearance < 40 mL/min (using the Cockcroft-Gault formula)
 - vi) AST/ALT: > 3.0 x ULN
 - vii) Total bilirubin > 1.5 x ULN (except participants with Gilbert Syndrome who must have a total bilirubin level of < 3.0x ULN)
 - viii) Any positive test result for hepatitis B virus or hepatitis C virus indicating presence of virus, e.g. Hepatitis B surface antigen (HBsAg, Australia antigen) positive, or Hepatitis C antibody (anti-HCV) positive (except if HCV-RNA negative).

4) Allergies and Adverse Drug Reaction

- a) History of severe hypersensitivity reactions to other monoclonal antibodies
- b) History of allergy or intolerance (unacceptable AEs) to study drug components or Polysorbate-80-containing infusions

5) Other Exclusion Criteria

- a) Prisoners or participants who are involuntarily incarcerated. (Note: under certain specific circumstances a person who has been imprisoned may be included or permitted to continue as a participant. Strict conditions apply and Bristol-Myers Squibb approval is required.
- b) Participants who are compulsorily detained for treatment of either a psychiatric or physical (e.g., infectious disease) illness

Eligibility criteria for this study have been carefully considered to ensure the safety of the study participants and that the results of the study can be used. It is imperative that participants fully meet all eligibility criteria.

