9.1 Efficacy Assessments

Study evaluations will take place in accordance with the Schedule of Assessment (Section 2). Baseline assessments should be performed within 28 days prior to first dose utilizing CT or MRI. In addition to chest, abdomen, pelvis, and brain, all known sites of disease should be assessed at baseline. Participants who cannot receive IV contrast for CT at the start of study should be imaged by MRI of abdomen/pelvis with IV contrast and CT of chest without contrast. Subsequent assessments should include chest, abdomen, and pelvis, and all known sites of disease and should use the same imaging method as was used at baseline. Participants initially imaged with CT of chest, abdomen, and pelvis with IV contrast who can no longer receive contrast can be monitored by CT of chest, abdomen, and pelvis without IV contrast. Please refer to additional precautions

regarding IV contrast in [Section 7.7.2.3](#). Participants in all cohorts will be evaluated for tumor response at the following intervals and time points:

- First tumor assessment should be performed at 12 weeks (± 1 week) following first dose. Subsequent tumor assessments should occur every 8 weeks (± 1 week) up to first 13 months, then every 12 weeks until disease progression or treatment discontinuation, whichever is later

For Cohorts 3 and 4: Brain lesion(s) that are < 10 mm or that have been previously irradiated will only be assessed as non-target lesion per RECIST 1.1. Brain lesions that are ≥ 10 mm and that have not been previously irradiated will be assessed as target lesions per RECIST 1.1.

Participants will be permitted to continue treatment beyond PD (RECIST 1.1) under protocol-defined circumstances (See [Section 7.9](#)). Tumor assessments for ongoing study treatment decisions will be completed by the investigator using RECIST (Response Evaluation Criteria in Solid Tumors) 1.1 criteria.

9.1.1 *Imaging Assessment for the Study*

Images will be submitted to the local lab, and read locally by the site Radiologist.

Table 9.1.1-1: Imaging Assessment Schedule (Cohort 1)

Study Day	Event Relative to Dosing	CT/MRI
Screening	Pre-dose	X
Week 12 (± 1 week)	Post-dose	X
Every 8 weeks (± 1 week)	Post-dose	X
Every 12 weeks (± 1 week), after Month 13 of treatment	Post-dose	X

Table 9.1.1-2: Imaging Assessment Schedule (Cohorts 2, 3 and 4)

Study Day	Event Relative to Dosing	CT/MRI
Screening	Pre-dose	X
Week 12 (± 1 week)	Post-dose	X
Every 8 weeks (± 1 week)	Post-dose	X

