3 RESPONSE CRITERIA

3.1 Evaluation of Target Lesions

Complete Response (CR): Disappearance of all target lesions. Any pathological lymph nodes (whether target or non-target) must have reduction in short axis to < 10 mm.

Partial Response (PR): At least a 30% decrease in the sum of diameters of target lesions, taking as reference the baseline sum diameters.

Progressive Disease (PD): At least a 20% increase in the sum of diameters of target lesions, taking as reference the smallest sum on study (this includes the baseline sum if that is the smallest on study). In addition to the relative increase of 20%, the sum must also demonstrate an absolute increase of at least 5 mm. (Note: the appearance of one or more new lesions is also considered progression).

Stable Disease (SD): Neither sufficient shrinkage to qualify for PR nor sufficient increase to qualify for PD, taking as reference the smallest sum diameters while on study.

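### An extracranial target lesion may be irradiated between the baseline scan and first dose, and no visible rule keeps its shrinkage out of the response assessment

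*Protocol*

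**What the plan says.** Two windows run back from first dose.

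- **Baseline scan.** Table 2-1 requires imaging of "all known sites of disease and MRI (preferred) or CT contrast-enhanced scan of the Brain within 28 days prior to first dose". Protocol 9.1 repeats the window: "Baseline assessments should be performed within 28 days prior to first dose utilizing CT or MRI". Neither place says that the scan must follow any radiotherapy. Protocol 9 also lets scans done as routine care before consent serve as baseline if they fall within the window.
- **Prior treatment.** Exclusion 2c in Protocol 6.2 (also in the Synopsis) sets two limits. The general one excludes "Anti-cancer therapy less than 28 days prior to the first dose of study drug". The shorter one excludes "palliative, focal radiation therapy less than 14 days prior to the first dose of study drug".

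The rule on irradiated lesions covers the brain only: "Brain lesion(s) that are < 10 mm or that have been previously irradiated will only be assessed as non-target lesion per RECIST 1.1" (6.1 item 2d, repeated in 9.1 for Cohorts 3 and 4). Item 2e of 6.1 adds that "Participant must have extracranial metastasis as measurable disease". Appendix 4 selects target lesions on size, organ representation and reproducibility, and does not mention irradiation. It defines PR as "At least a 30% decrease in the sum of diameters of target lesions, taking as reference the baseline sum diameters".

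SAP 4.2 defines BOR, PFS 1 and DOR with rules for anti-cancer therapy that comes after study treatment starts, but none for radiotherapy before first dose. SAP 7.3.4 tabulates prior radiotherapy as yes or no and plans a by-subject listing.

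**The concern.** For general anti-cancer therapy, the washout and the scan window are both 28 days, so a baseline scan inside its window cannot predate that therapy. Palliative focal radiotherapy is the exception. A participant scanned on day -28 and irradiated at a painful extracranial site between then and day -14 meets every visible rule, and the baseline sum is a pre-radiation sum.

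If the irradiated lesion is a target lesion, its later shrinkage enters the comparison with baseline and is credited to nivolumab plus ipilimumab. There is no control arm to offset the error. The protocol already accepts the principle for the brain. The safeguard is missing at extracranial sites, where every participant must have measurable disease.

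**Working it through.** **The plan's own figure.** The only design precision given (Protocol 10.1, SAP 5) is the half-width of the 95% CI for a high-grade IMAE rate. With 1.96 × √(p(1−p)/n), n=100 gives 9.28 points at p=0.34 and 9.80 at p=0.50; n=200 gives 6.57 and 6.93. The stated ranges (9.3 to 9.8 and 6.6 to 6.9) reproduce. The present point does not depend on them. The same formula at n=25 gives 18.6 to 19.6 points over that range of p, which is a useful scale for the ORR shifts below.

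**Gap between the windows.**
- Earliest permitted baseline scan: day -28 (Table 2-1, 9.1).
- Latest permitted palliative focal radiation: day -14 (6.2 item 2c).
- Interval in which radiation can follow the scan: 28 − 14 = 14 days.
- For general anti-cancer therapy: 28 − 28 = 0 days.

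**Would shrinkage be seen?** The first on-study scan is at week 12 ± 1, that is days 77 to 91. From radiation on day -14 to a scan on day 77 is (14 + 77)/7 = 13 weeks. From the start of the gap to day 91 is (28 + 91)/7 = 17 weeks. A radiation effect could be visible by then.

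**How much shrinkage gives PR?** With k equal target lesions, one of them irradiated and the others unchanged, a 30% fall in the sum needs that lesion to shrink by 30% × k:

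| Equal target lesions | Shrinkage needed in the irradiated lesion |
|---|---|
| 1 | 30% |
| 2 | 60% |
| 3 | 90% |
| 4 | 120% (impossible alone) |
| 5 | 150% (impossible alone) |

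With four or five equal lesions, the irradiated one can only add to shrinkage elsewhere.

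**Effect of one misattributed response on ORR.** 1/100 = 1 point in Cohort 1, 1/50 = 2 points in Cohort 2, 1/25 = 4 points in Cohort 3 or 4. SAP 7.5.1.2 uses response-evaluable subjects, so a smaller denominator would make each step slightly larger.

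**Assumed range.** The documents give no frequency. If 2% to 10% of participants were irradiated in the gap, and 10% to 50% of those reached PR only because of it, ORR would rise by 0.02 × 0.10 = 0.2 points up to 0.10 × 0.50 = 5.0 points. Both ranges are assumptions.

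**Which endpoints.** ORR and TTR rest on the fall from the baseline sum, and DOR includes only confirmed responders, so all three can be touched. Target-lesion progression is referenced to the smallest sum on study, so radiation shrinkage reaches PFS 1 only through that reference. The primary endpoint, high-grade IMAEs, does not use tumor measurements.

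**The case against.** The strongest reply is that the protocol handles the likeliest case. Item 2d(ii) of 6.1 foresees brain metastases found at screening, treated, and the participant "will be re-enrolled to Cohort 3 or 4 (depending on the KPS level) after completing active treatment". A reader might infer that the error therefore concentrates in Cohort 3 and the brain-metastasis participants of Cohort 4, and that 1 to 3 false responders among 25 would inflate ORR there by 4 to 12 points. The documents do not support this. Irradiated brain lesions are non-target, so their shrinkage cannot produce the 30% fall in the target sum, and the 1 to 3 has no source. Protocol 6.4.1 requires re-consent on re-enrollment. It does not expressly order a new scan, but reuse of the old one is not shown either. One doubt remains: the text does not say whether previous irradiation of a brain lesion is judged at the scan or at first dose.

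It is also fair to say that outside the brain only palliative focal radiation is allowed in the gap, that the lesion must be a target lesion, and that the response must be confirmed at least 28 days later. Confirmation removes transient readings, but it does not correct the attribution.

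Protocol 7.7, which includes the section cited for contrast precautions in imaging, is blacked out. A rule on irradiated lesions could stand there; none is visible elsewhere.

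Finally, this is a safety trial with descriptive efficacy, and at n=25 one response is small beside a half-width near 19 points. That limits the importance of the point but does not close the gap.

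**Conclusion.** The point holds in a narrow form. The windows leave 14 days in which an extracranial target lesion can receive palliative focal radiation after the baseline scan, and no visible rule prevents its shrinkage from contributing to a PR. It would go too far to say that radiation shrinkage simply counts as drug response: the lesion must be a target, the whole sum must fall by 30%, and the fall must be confirmed. It would also go too far to say that PFS 1 is distorted in the same direct way.

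The size is 1, 2 or 4 ORR points per misattributed response at the planned n of 100, 50 or 25. The number of such responses cannot be derived from the documents; under the assumed ranges the inflation is 0.2 to 5.0 points. The conclusion rests on there being no contrary rule in the blacked-out text. Only descriptive secondary endpoints are touched. This is a cheap improvement in attribution, not a flaw in the trial's main purpose.

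**What to change.** **Protocol 9.1 and Appendix 4.** Extend the existing brain-lesion rule: any lesion irradiated before first dose, including between the baseline scan and first dose, is assessed as non-target. State that for brain lesions previous irradiation is judged at first dose.

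**SAP 4.2 and 7.5.1.2.** Add an ORR sensitivity analysis that excludes participants irradiated between the baseline scan and first dose. The prior-radiotherapy listing planned in SAP 7.3.4 can identify them, provided that it carries treatment dates. If enrollment is already complete, this part remains available.

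**Cost.** The change needs wording and a little more analysis work. A few participants may have fewer target lesions, or none, and so contribute less to ORR. The eligibility criteria and the radiotherapy window need not change, and no repeat scan is required.
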